Traditional methods of orbital fractures reconstruction involve intra-operative shaping of orbital implants (titanium mesh). ⁽¹⁰⁾ Orbital fracture reconstruction using selective laser-melting patient-specific implants has been found to be superior to traditional reconstruction methods. ^(8, 11, 12) The challenges with the traditional approach are a significant increase in cost and longer preoperative time (production time). ^(11, 12) There have been no comparisons published between the traditional approach and pre-adjusted patient-specific orbital implants with respect to orbital volume reconstruction.

- Hypothesis #1: Pre-adjusted patient-specific orbital implants will **more accurately restore the orbital volume** to pre-trauma measures than non-patient-specific orbital implants.

Aim #2: To compare postoperative complications.

The main complications due to orbital fractures reconstruction are 1) enophthalmos and 2) diplopia as a result of inadequate orbital volume reconstruction. The incidence of enophthalmos after the traditional orbital reconstruction approach is 7–27%. ^(5, 13, 14) This rate is significantly higher than that observed after using the patient-specific approach (3.7%). ⁽¹²⁾ Again, there are currently no data regarding pre-adjusted, patient-specific orbital floor implants. The incidence of

diplopia after the traditional orbital reconstruction approach is 8–42%,^(14–16) which is significantly higher than that for the patient-specific approach (3.2%).⁽¹²⁾

- **Hypothesis #2:** Pre-adjusted patient-specific orbital implants will **have fewer postoperative complications** than non-patient-specific orbital implants.

Aim #3: To evaluate the length of hospital stay. The typical hospital stay for an orbital floor fracture at Grady Memorial Hospital (GMH) is 1–2 days, depending on the patient's response to surgery.

- **Hypothesis #3:** Pre-adjusted patient-specific orbital implants lead to a **shorter length of stay**, secondary to improved accuracy of implant design, placement, and reduced need for manipulation. This would be expected to lead to decreased postoperative swelling and pain. Orbital fracture reconstruction could be executed as a same-day surgery (outpatient surgery) when utilizing 3DP.

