The primary outcome variable is the orbital volume of the injured orbit compared to the contralateral uninjured orbit as assessed by CT scan with OsiriX medical imaging software (OsiriX MD 8.5.2) **at immediate post-operative hour**.

Accordingly, the primary outcome variable will be classified as:

- A. The absolute reduction in orbital volume from the measured post-traumatic volume, as measured by CT.

The secondary outcome variables will be recorded 1 week, 3 weeks, and 6 weeks postoperatively.

The secondary outcome variables include the following:

- 1- Adequate orbital volume reduction, defined as a reduction of orbital volume to **less than 2 cm³**.
- 2- Unsatisfactory orbital volume, defined as a final orbital volume **more than 2 cm³**
- 3- Post-operative variables: enophthalmos, infection, infraorbital nerve injury, traumatic pupillary mydriasis, orbital compartment syndrome, extra-ocular motility, and plate contour.
- 4- Operating time.
- 5- Length of stay (LOS).
- 6- Treatment charges.

The following are details regarding secondary outcome variables:

- Enophthalmos as assessed by clinical examination using a Hertel exophthalmometer.
 - A difference of more than 2 mm between the two orbits is diagnostic for enophthalmos.⁽⁴⁾
- Infection
 - As defined by the presence of post-operative pus in the wound, a sinus tract or fistula, or elevated WBC >11.0x10⁹/L combined with erythematous skin and swelling on the operated side more than on the un-operated side.
- Infraorbital nerve injury as assessed by clinical examination using neurosensory testing (NST).
 - i. NST is a standardized methodology designed to objectively evaluate sensory nerve function.⁽²²⁾ The sensory impairment is determined by 3 levels of testing; each level classifies a specific type of sensory nerve injury.^(22, 23)
 - ii. All patients will be assessed for the development of altered sensation of the infra-orbital nerve that:
 - A. Did not present prior to the surgery.
 - B. Did not improve after the surgery.
- Traumatic pupillary mydriases as assessed by pupillary size measurement in millimeters.
 - All patients will be assessed for the development of post-operative traumatic pupillary mydriasis that did not present prior to the surgery.
- Orbital compartment syndrome as assessed through clinical examination using tonometers.
 - Intra-ocular pressure (IOP) > 40 mmHg is diagnostic of orbital compartment syndrome.

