- Extra-ocular motility as assessed through clinical examination. The patient should be able to move the eyes through the six cardinal positions of gaze (left, right, up and right, up and left, down and right, down and left). All patients will be examined for the following:
 1. Development of restricted extraocular motility that was not present prior to the surgery.

2. Persistent restriction of extraocular motility after the surgery.

- Plate contour
 - Inability to achieve the normal orbital contour as assessed in the immediate post-operative CT scan.
- Operating time
 - This will be calculated from fracture exposure and identification to the final implant placement and fixation and will be recorded in minutes.
- Length of stay
 - 1- Isolated orbital floor fracture patients do not require a pre-operative hospital stay. Length of stay will be calculated in terms of post-operative hospital stay (days).
 - 2- Length of stay in cases of complex orbital fracture will be calculated in terms of pre-operative and post-operative hospital stay (days).
- Treatment charges

This will be calculated with consideration of the following:

- 1- Facility operating room charges, which include anesthesia time (surgical time multiplied by the facility rate of \$33/ minute).
- 2- Hardware charges (plates and screws).
- 3- LOS charges (LOS multiplied by the facility daily rate of \$1,690/ day).
- 4- The cost of the 3D printed model including the cost of the 3D printer and filaments (\$1.5).

All treatment charges variables will be provided by the GMH Financial Planning and Analysis center. Total treatment charges facility operating room charges, hardware charges, LOS, and the 3D printed model cost will be compared between groups in a manner similar to that outlined by Bouloux et al. ⁽²⁴⁾

Randomization Sample Size & Calculation

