The success of the randomization will be evaluated at the start of the analysis by comparing patient characteristics. Differences between the treatment and control arms that do not reach statistical significance using appropriate tests (likely t-tests and chi-square tests) that are smaller than 20% for all characteristics will mean that the groups are ‘balanced’ in our criteria and will be evidence of randomization success. Assuming that standardization is successful, all outcomes will be compared using standard two-sample comparisons. For binary outcomes, such as complications and CT use, Chi-square tests or Fisher’s exact tests will be used depending on the prevalence of the outcome. Two-sample t-tests or Wilcoxon-Mann-Whitney tests (if data are non-parametric) will be used to compare mean orbital volume differences and operative times. Differences in length of stay and costs are likely to be analyzed with two sample t-tests on a log scale (thus, a comparison of geometric means will be made). Finally, logistic regression or other multivariable analyses may be performed to identify risk factors for developing complications or deviations from the normal recovery course.

Statistical Support

Support for statistical analyses will be provided by [name], MSPH, a trained biostatistician, working for the Department of Surgery at Emory University Hospital. All analyses will be conducted or supervised by [name]. [name] has 15 years of experience in data analysis and 7 years of experience working as the department statistician for surgery. He has over 40 peer-reviewed publications to his name and experience with outcomes and health services research as well as basic science research. In the past, he has assisted in the design and analysis of similar trials at Emory University. Regarding the cost-effective analysis, [name] is the primary mentor. He is an experienced researcher and participated in cost-effective research in GMH by comparing the cost effectiveness of 2 types of mandibular fracture treatment. ⁽²⁴⁾

Inclusion & Exclusion Criteria

- The following subjects will be included in the study:
 - 1- Agreed to be enrolled in the study.
 - 2- Indications for surgical repair of orbital floor and/ wall fractures are dependent on several factors:
 - a. Correction or prevention of cosmetic deformity (enophthalmos or inferior dystopia; disruption of greater than 50% of the orbital floor is likely to cause cosmetically apparent enophthalmos.

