Data	Time
Age, sex, race, DOB	Pre-operative (pre-op)
Mechanism of injury, time from injury to admission	Pre-op
Type of orbital fracture and other injuries	Pre-op
Indications for surgery	Pre-op
CT scans results (fracture size & location)	Pre-op
Extra-ocular motility indicating which gaze	Pre-op
Level of infraorbital nerve injury	Pre-op
Traumatic pupillary mydriasis	Pre-op
IOP (Intra-ocular pressure)	Pre-op
Enophthalmos (Hertel exophthalmometer measurement)	Pre-op
The use of 3D printed models	Pre-op
The time needed to print the model	Pre-op
Orbital and ocular exam results	Pre-op
Time from admission to surgery	Pre-op
Date of surgery	Pre-op
Length of surgery (minutes)	Operative
Approach	Operative
Intra-operative complications	Operative
Post-operative orbital volume comparison (OsiriX)	Post-operative
Dates of post-operative visits	Post-operative, weeks 1, 3, and 6
Extra-ocular motility indicating which gaze	Post-operative, weeks 1, 3, and 6
Level of infraorbital nerve injury	Post-operative, weeks 1, 3, and 6
Traumatic pupillary mydriasis	Post-operative, weeks 1, 3, and 6
IOP (Intra-ocular pressure)	Post-operative, weeks 1, 3, and 6
Infection	Post-operative, weeks 1, 3, and 6
Enophthalmos (Hertel exophthalmometer measurement)	Weeks 1, 3, and, 6

Overall cost	Post-operative
Need for second surgical procedure	Post-operative, weeks 1, 3, and 6

SIGNIFICANCE AND INNOVATION

This project will test two new and evolving methodologies in the medical world: 1) an office-based 3D printer and 2) pre-adjusted patient-specific implants. These two methodologies have yet to be applied together in orbital fracture reconstruction. Additionally, this study focuses on low-income patients and will be the first of its kind serving this population. Several other benefits include potential savings related to total overall cost, a reduced operative time and postoperative course, and a subsequent increase in both the quality of care and the value of care, especially in the underserved patient population cared for at GMH. We expect the results of this study to be applicable at most major urban trauma centers across the USA and abroad. The results of this study can be used in future studies as a model or pilot study.

FUTURE PLANS

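### New and persistent eye-motility deficits (and probably infraorbital nerve deficits) are compared between arms without using the recorded pre-operative status, which leaves chance imbalance in part of Aim 2 and can lose power

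*Combined protocol and SAP*

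**What the plan says.** The details of the secondary outcomes (Methodology, Study Settings and Patients) give two motility items: "Development of restricted extraocular motility that was not present prior to the surgery" and "Persistent restriction of extraocular motility after the surgery". For the infraorbital nerve, patients are assessed for the development of altered sensation that, item A, "Did not present prior to the surgery" and, item B, "Did not improve after the surgery". No conjunction joins A and B. Mydriasis is limited to new onset: "post-operative traumatic pupillary mydriasis that did not present prior to the surgery".

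The Data Collection & Analysis table records "Level of infraorbital nerve injury" and motility by direction of gaze, both before surgery and after it (weeks 1, 3 and 6).

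Under Randomization & Statistical Analysis, provided randomization is judged successful, "all outcomes will be compared using standard two-sample comparisons", with Chi-square or Fisher tests for complications. Success means non-significant differences below 20% on all characteristics. No method is given for the case where this fails. Multivariable analysis is optional and aimed at risk factors. Randomization is stratified by surgeon/specialty only.

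Aim #2 hypothesises that the pre-adjusted implants will "have fewer postoperative complications".

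**The concern.** Some patients will arrive with a deficit. Muscle incarceration is itself an indication for surgery in the inclusion criteria. A patient with restricted gaze before surgery can have the persistent event. A patient without it can have only the new event. These two risks are likely to be very different, so the event rate in an arm depends heavily on how many of its patients arrived with a deficit.

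An unadjusted comparison of whole arms leaves that chance variation in the estimate although the variable that explains it is in the database. A reported difference in complications then mixes three things: harm from surgery, failure of the injury to resolve, and who happened to arrive with the deficit.

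**Working it through.** **The plan's own figure.** The documents give a sample size only for the volume outcome: a difference of 1 cm³, SD 1.17 cm³, alpha 0.05 (taken as two-sided) and 90% power. The normal formula gives 2 × 1.17² × (1.960 + 1.282)² / 1² = 28.8, so 29 per arm. The exact t calculation gives 90.2% power at 30 per arm and 80.0% with 45 patients (22 and 23). Both stated figures reproduce. No power is stated for complications.

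**Inputs for the check.** 30 per arm is from the plan. Prevalence of the pre-operative deficit, persistence and new-onset rates are assumptions, because the documents give none.

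**1. How often the arms differ at baseline.** With two independent binomial counts of size 30, the chance that they differ by 6 or more patients (20 points) is:
- 12.0% at prevalence 30% or 70%
- 14.7% at 40% or 60%
- 15.5% at 50%

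**2. What the imbalance does to the estimate.** With no treatment effect, expected shift = baseline difference × (persistence − new onset).
- 20 points, persistence 60%, new onset 5%: 0.20 × (0.60 − 0.05) = 0.11, or 11 points.
- 20 points, persistence 30% to 80%: 0.20 × 0.25 = 5 points, up to 0.20 × 0.75 = 15 points.
- A five-patient difference (5/30 = 16.7 points): 0.167 × 0.55 = 0.092, or 9 points. At 50% prevalence its z value is 0.167 / √(2 × 0.25/30) = 1.29, so it is non-significant and below 20%. It passes the balance check.

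**3. Type I error (simulation, no treatment effect, new onset 5%).** Over all randomizations the Chi-square test rejects 4.7% to 5.5% of the time. In trials with a 20-point imbalance it rejects about 5% to 17% of the time, against 4% to 6% for a Mantel-Haenszel test stratified by pre-operative deficit. The ends of these conditional ranges are rough.

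**4. Power (simulation, 40,000 runs, new onset 10% control and 5% treated).**

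| Pre-operative prevalence | Persistence, control vs treated | Unadjusted Chi-square | Stratified | Loss (points) |
|---|---|---|---|---|
| 30% | 50% vs 25% | 21% | 23% | 2 |
| 50% | 50% vs 25% | 28% | 32% | 3 |
| 70% | 50% vs 25% | 37% | 40% | 3 |
| 30% | 80% vs 40% | 29% | 40% | 11 |
| 50% | 80% vs 40% | 45% | 61% | 16 |
| 70% | 80% vs 40% | 65% | 77% | 12 |

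Losses are taken before rounding. With 5% new deficits in both arms and 50% prevalence, persistence of 60% vs 25% gives 35% unadjusted and about 43% stratified; 80% vs 40% gives about 37% and 53%.

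These stratified figures use no continuity correction. With the correction, the last two become 29% and 39%, so the gain is lost or nearly so.

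**5. If the implant affects new deficits only (30% vs 5%, equal persistence of 30% to 80%).** Stratifying gains about 0 to 14 points. Combining the two events itself costs more: Chi-square power falls from 60% for new deficits alone to 29–38% for the combined outcome (prevalence 30%), from 43% to 17–20% (50%), and from 19% to 9–10% (70%). Conversely, when persistence is what differs (step 4), new deficits alone give 6% power or less. Neither event should be dropped, and both should be visible.

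**The case against.** **The nerve item may not count pre-existing numbness.** It speaks of the development of altered sensation, and A and B carry no conjunction. Read jointly they describe new numbness that does not resolve. This stands as a real ambiguity. The parallel motility list makes the alternative reading more likely, but a reader should not take it as settled.

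**Merging is not stated.** The motility items are numbered separately, and nothing says they become one yes/no variable. This also stands: the concern about the combined test is conditional on that choice, which the plan leaves open.

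**The unadjusted test is conditional on balance.** An imbalance of 20 points or more would fail the check, if pre-operative deficit is among the characteristics compared and the 20% means percentage points. The plan settles neither. Even so, differences just under the limit pass, and a failed check leads to no named analysis.

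**There is no bias.** A reader might infer that the unadjusted test inflates false positives. It does not: chance imbalance is already part of its null variance, and overall type I error is about 5%.

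**Dilution.** A reader might also infer that patients who cannot have the event dilute the comparison. In a combined outcome every patient can have one of the two events, so that argument fails. Nor are the risk sets strictly separate: a patient restricted in one gaze can develop restriction in another.

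**The gain is assumed and may be small.** Correct. It is about 1 to 4 points under more modest effects, and power is low for these items either way.

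**Conclusion.** The point holds as a matter of precision and clear definition. The motility outcome includes persistence of a pre-operative deficit, the nerve outcome probably does too, and no planned treatment comparison uses the pre-operative status that is recorded for both. If each pair is analysed as one complication, chance imbalance stays in the estimate (about 11 points for a 20-point imbalance at 60% persistence and 5% new onset). The power lost against a stratified test runs from near 0 to about 16 points. Those sizes rest on assumed prevalence, persistence and new-onset rates, and on a Mantel-Haenszel test without continuity correction.

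The documents do not support a claim of systematic bias, of inflated overall type I error, or that pre-operative numbness is certainly counted as a complication. The reach is also limited. Aim #2 names enophthalmos and diplopia as the main complications, so this touches part of Aim #2, and the primary volume outcome and its sample size are unaffected. It is worth changing because the remedy is nearly free.

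**What to change.** 1. State whether nerve items A and B are alternatives or must both be met, and whether the two motility items form one variable.
2. For each outcome, report new deficits among patients without that deficit before surgery, and unresolved deficits among patients with it.
3. Compare the arms on the combined outcome with a Mantel-Haenszel test without continuity correction, or a logistic model, stratified by pre-operative status. Specify this in advance, whatever the balance check shows.
4. Count worsening of nerve level, or restriction in a new gaze, in patients who already had a deficit. The recorded level and gaze allow this.

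Cost: a few sentences in the analysis plan and no new data. The separately reported rates have smaller denominators and so wider intervals.

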There are 2 main approaches to orbital fracture management. The traditional approach involves the use of a standard stock orbital plate, which is adapted intraoperatively to the fractured orbit. The advantages of this approach are that the plates are readily available, cheap, and require minimum peri-operative planning. The major drawback of the traditional approach is the inaccurate nature of reconstruction. It is often challenging to restore the orbital volume using this approach, and failure to restore volume results in post-operative enophthalmos.⁽¹²⁾ The second approach uses CAD/CAM technology (computer-aided design/computer-aided manufacturing technology). In this approach, a virtual plan is developed based on the patient's

CT scans. A 3D stereolithographic model is then fabricated, and a patient-specific titanium orbital implant is manufactured. These implants are manufactured using a selective laser melting process (KLS Martin, Tuttlingen, Germany). ^(11, 12) The CAD/CAM technology is currently considered to be the most accurate method of orbital reconstruction. ^(11, 21) The advantage of this approach is that it is patient-specific and therefore very accurate. However, the CAD/CAM technology is exceedingly expensive (depending on the vendor from \$6,995 to \$10,956.40 per case) with long production times (7–14 days). Reconstruction of the orbital fracture is time-sensitive to prevent unfavorable long-term sequelae; thus, CAD/CAM technology in orbital fractures has limitations due to production time. The second limitation of this approach is the cost. Fortunately, this technology is available today at a **low cost and high resolution due to office-based three-dimensional printing (3DP)**.

In this study, we propose a third approach to manage orbital fractures. This approach involves a **patient-specific pre-adjusted (pre-bend) orbital plate** utilizing an office-based 3DP. The approach is patient-specific because the orbital plate is preoperatively adjusted (pre-bend) to the patient's anatomic model; **this decreases the OR time and increases the accuracy of reconstruction**. The cost of 3D printing the patient's fractured orbital floor in the office is **significantly less than** the cost of utilizing the CAD/CAM technology for one patient. **The 3D printed model will cost at most \$1,374.5 (\$1.50 printed model + \$1,364 for the stock titanium implant) vs. \$2,800 for VSP utilizing a stereolithographic model with a patient-specific implant.**

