 - 1) The Digital Imaging and Communications in Medicine (DICOM) image of the pre-op CT scans will be processed using the 3DP computer software to create mirror imaging of the un-injured bony orbit over the fractured orbit. This imaging will be utilized to print a 3D anatomical model. The 3D printing for the enrolled subjects will be performed by [name] and [name]. This will ensure accuracy and limit bias. [name] and [name] are trained to operate the 3D printer software and will follow a standardized approach.

The standardized approach to 3D printing:

- a- A 3D slicer. This is the first software used. Its functions are:
 - Identify the area of interest.
 - Segment the CT DICOM image.
 - Convert the DICOM file into an STL file.
- b- Meshmixer is the second software used. Its functions are:
 - Clean up the printed image.
 - Convert the image to a solid format to facilitate the 3D printing process.
 - Plane cuts and image mirroring.
- c- The third software is the printer's designated software. It facilitates the printing process.

- 2) Once an anatomical model is created, a titanium mesh will be pre-adjusted to the anatomical model. This step will be performed by the designated surgical team and supervised by one of the following attending ([name] for OMFS, [name] for ENT, or [name] for Plastic Surgery). To optimize standardization and reduce bias, the surgical team will standardize the type of orbital plate by using one vendor (Stryker) and will follow the following guidelines to bend the orbital plates:
 - Identify the fracture dimension and location on the printed model.
 - Choose the titanium plate according to the defect dimension.
 - Start bending the plate from the lateral to medial direction. Doing this ensures that defects in the edges overlap and that the fractured bone (defect) is adequately covered.
 - The defect edges are overlapped by 2 mm of the titanium plate.
- 3) The pre-adjusted titanium mesh will be sent to the sterile processing department to be utilized in surgery.

Intra-operative Assessment: Procedures & Treatment

- All operations will utilize general anesthesia.
- A forced duction test of the injured eye will be performed after induction and before extubation in all cases to ensure no entrapment of extra-ocular muscles as the standard of care indicates in these cases.
- All isolated orbital floor fractures will be exposed and identified via a transconjunctival approach.

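### The Aim 4 cost comparison does not list preparation resources used only in Group A, so it leans toward Hypothesis 4 by an amount the documents do not allow us to calculate

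*Combined protocol and SAP*

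**What the plan says.** Under Methodology, the Treatment charges item has four lines:

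- operating-room charges, given as "surgical time multiplied by the facility rate of" $33 per minute;
- hardware;
- length of stay at $1,690 per day;
- "The cost of the 3D printed model including the cost of the 3D printer and filaments", with $1.5 in brackets.

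The total to be analysed has the same four parts: "facility operating room charges, hardware charges, LOS, and the 3D printed model cost will be compared between groups". On the source, the plan says "All treatment charges variables will be provided by the GMH Financial Planning and Analysis center". Operating time is a separate outcome: "This will be calculated from fracture exposure and identification to the final implant placement and fixation".

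The Group A work-up under Preoperative Assessment describes steps that control patients do not have. CT images are segmented and mirrored and a model is printed by two trained operators. The surgical team bends the plate to the model under an attending. Then: "The pre-adjusted titanium mesh will be sent to the sterile processing department to be utilized in surgery". The end of the Background also mentions the sterilization step. The Data Collection table records "The time needed to print the model", but nothing turns that time into a cost.

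Aim 1 and the Background say that the traditional plate is shaped during the operation. Aim 4 concerns overall cost, and Hypothesis 4 is that the pre-adjusted implant is cheaper.

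**The concern.** The mechanism behind Hypothesis 4 is that shaping work moves out of the operating room and so shortens the operation. The charge definition records the theatre time saved. It has no line for the work that replaces it, apart from $1.5 for the model. Each resource missing from the list is one that only Group A uses, so the omissions cannot cancel between arms.

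A finding that Group A costs less would then rest partly on what was left out of the total. This matters because the protocol presents lower cost as a main benefit of the method, and Future Plans links its use to lower overall health care cost. Staff time is also hard to reconstruct afterwards, so a gap in collection cannot easily be repaired at analysis.

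**Working it through.** **The plan's own figure.** The Background says "The 3D printed model will cost at most" $1,374.5, itemised as $1.50 for the model and $1,364 for the stock implant.

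- $1.50 + $1,364 = $1,365.50.
- $1,374.5 − $1,365.50 = $9.00, so the stated sum does not reproduce.
- The itemised model price of $1.50 agrees with the $1.5 in the Treatment charges list. Only the addition is wrong.

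**What each arm is charged for.**

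| Resource | Control | Group A |
|---|---|---|
| Shaping the plate | During surgery, in charged time | Before surgery, no line |
| Segmentation and mirroring | Not used | No line |
| Printing, operator time | Not used | No line |
| Model, printer and filament | Not used | $1.5 |
| Sterile processing of the bent plate | Not used | No line |

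The charge line does not say whether its surgical time is the same interval as the operating-time outcome. Shaping done during surgery to fit the fractured orbit should fall inside either one.

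**Inputs from the documents.** The rate is $33 per minute. There are 60 cases split evenly, so 30 in Group A. The model is $1.5. The cited operating-time saving is 0.40–3.82 h, and Aim 4 gives it for selective laser-melted implants.

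- Model charge in theatre time: 1.5 / 33 × 60 = 2.7 seconds.
- Model charge over the trial: $1.5 × 30 = $45.
- Ten minutes of shaping: 10 × $33 = $330 if done in theatre, $0 if done beforehand.
- Low end of the cited saving: 0.40 × 60 × $33 = $792.
- High end: 3.82 × 60 × $33 = $7,564 (rounded).

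**Possible size, by assumption only.** The documents give no labour, sterilization or printer price.

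- Assume 2–5 staff hours at $30–$100 per hour: 2 × $30 = $60, and 5 × $100 = $500.
- Against $792: 60 / 792 = 8%, and 500 / 792 = 63%.
- Against $7,564: 60 / 7,564 = 0.8%, and 500 / 7,564 = 6.6%.
- The full range is about 1–63%.

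A second set of assumptions shows how much the answer depends on the inputs. Take 1–4 hours at $30–$150 per hour ($30–$600), sterile processing at $25–$100, and a $500–$5,000 printer spread over 30 cases ($17–$167).

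- Low: 30 + 25 + 17 = $72. High: 600 + 100 + 167 = $867.
- In theatre time: 72 / 33 = 2 minutes, and 867 / 33 = 26 minutes.
- The upper value would exceed the $792 saving. It would be about 11% of $7,564.

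**The case against.** The strongest defence is perspective. The outcome is called treatment charges, it uses facility rates, and the hospital finance center supplies the data. Neither arm has a line for professional fees. From a facility-charge viewpoint, unbilled staff time may be left out by choice, and adding wages and a share of equipment mixes costs with charges. This stands in part. The plan never states a perspective: Aim 4 says overall cost, Hypothesis 4 says operative cost, and the outcome is charges. By naming the printer, the fourth line itself brings a preparation resource into the total.

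Sterile processing of the bent plate may already sit inside facility or hardware charges. The documents do not say, nor do they say how control plates are sterilised. The extra cost is therefore unknown and should not be asserted.

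A reader might infer three stronger points that the documents do not support.

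- *That charging control shaping at the theatre rate is itself a fault.* It is not, because that time is really used. The gap is that the matching Group A work has no line.
- *That the printer is certainly left out, or that the Background contradicts the $1.5.* The bracket may belong to filament alone, with the printer amount simply not given. The Background itemises the model at the same $1.50, and its $9 slip is separate.
- *That most of a low-end saving would be used up.* That rests on assumed labour and on one end of a saving cited for a different technology.

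**Conclusion.** The concern holds for direction. As listed, the Aim 4 total omits segmentation and mirroring, operator time for printing and pre-operative bending, and it does not say where sterile processing of the bent plate is charged. These resources belong to Group A alone, so the comparison leans toward Hypothesis 4.

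The size cannot be found from the documents. The 1–63% range rests on assumed labour of $60–$500 per case and on a borrowed time saving. A large true saving in operating time could outweigh the omission, so it does not follow that a favourable cost result would be false.

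The $1.5 needs explaining on either reading. As worded it includes the printer, which is not credible at $45 over 30 cases. If it is filament only, the printer amount is missing.

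This affects a secondary outcome. The primary orbital-volume comparison is untouched.

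**What to change.** 1. State the costing perspective for Aim 4, and use one term in the aim, the hypothesis and the outcome.
2. Log staff time prospectively in Group A for segmentation, printing and bending. The recorded print time is not enough, because the plan does not say that staff attend the printer throughout.
3. Ask the finance center whether sterile processing of the bent plate is already in facility or hardware charges, and add a line if it is not.
4. State $1.5 as filament only, and add printer cost divided by the number of cases printed.
5. Report Aim 4 with and without these items, adding them to each Group A total before any log transformation.

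Two minor corrections belong alongside. Correct the Background sum to $1,365.50, or explain the other $9. Reconcile the description of control implants as non-adapted (Abstract and end of Background) with the statements that they are shaped during surgery (Aim 1 and Background).

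The burden is a short log for about 30 cases and two extra lines from finance. The drawback is a cost result less favourable to Group A.
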